19. QRS \geq 0.18 seconds noted \geq 6 days after the onset of MI.
20. * WPW syndrome.
21. * Congenital long QT syndrome.
22. Prolonged pause of \geq 2.5 seconds noted \geq 6 days after the onset of MI.
23. Mobitz II 2nd degree, advanced or 3rd degree AV block noted \geq 6 days after the onset of MI.
24. Symptomatic sinus node dysfunction.
25. Heart rate $<$ 30 beats per minute for a period lasting at least one minute noted \geq 6 days after the onset of MI.

Drug Therapy

26. Previous serious adverse effect from drug(s) used in CAST.
27. On concurrent antiarrhythmic drug therapy, excluding digitalis, beta blockers, and calcium channel blockers.
28. Any intravenous or oral amiodarone within the last 2 weeks.
29. Any oral amiodarone within the last 6 months.
30. Intravenous amiodarone for \geq 48 hours within last 6 months.

Holter Findings

31. Symptomatic (hemodynamically important) unsustained VT or VT \geq 15 consecutive complexes at a rate \geq 120 beats per minute (disqualifying VT) noted \geq 6 days after the onset of the myocardial infarction (noted on Holter).
32. Insufficient arrhythmia ($<$ 6 VPD's/hr) on both screening Holters.

Miscellaneous

33. Psychologically or physically unfit to participate in the study.
34. Patient is geographically inaccessible.
35. Interpretation of Holter technically difficult.
36. Patient enrolled in a competing interventional trial, e.g., undergoing blinded therapy. Participation in followup after intervention is completed (e.g. thrombolytic trials) may be permissible and will be decided by the Executive Committee on a study by study basis.

C. Recruitment/Screening

Screening Log

Centers will be required to maintain a screening log for all patients identified who are age and CAST MI eligible patients. This log will include minimal information: name, age, sex, date of CAST MI, and principal reason for exclusion when applicable. Data entry will include a log number but not the name.

Holter Registry

A registry will be maintained for all consenting patients who are medically eligible, i.e., are not excluded by any of the *'d exclusions. Patient identifying information, consisting of name, date of birth, social security or other identifying number, and sex will be obtained together with the Holter findings and EF if available (see Appendix 4).

D. Stratification for Randomization

Stratification for randomization will be done on the following variables:

1. Clinical center
2. Left ventricular ejection fraction.

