A Holter is required at each drug and each dose evaluation unless adverse effects are noted, including an ECG exclusion noted on an arrhythmia monitor. ECG intervals throughout dosing will be measured and documented via a Holter rhythm strip. Submission of Holter data is required to document suppression as defined above or at least minimal suppression on the best drug and dose when 80% suppression is not obtained. When a Holter is obtained that does document suppression, as defined above, titration is to cease at that point, and the drug and dose the patient is suppressed on will be the designated drug and dose for that patient. The Holter tape documenting suppression or best drug and dose (in addition to the qualifying Holter) must be kept at the center until the end of the study.

G. Conditions Requiring Specific Actions during Titration.

1. Conditions requiring permanent cessation of titration. (This patient would not be randomized to blinded therapy and would not be followed as a patient in the main CAST study.)

a. The appearance of any entry exclusion criteria proven by washout not to be due to drug toxicity with the exceptions explained and described below:

Certain of the exclusion criteria were included because they were thought to yield a high probability that with the addition of active CAST therapy a safety concern would emerge. However, once a patient has agreed to participate and even entered titration there is no reason to exclude the patient unless the limit for concern is achieved. For this reason criteria 19, 21, and 22 are modified to:

QRS \geq 0.20 seconds

QTc \geq 0.6

Any pause of \geq 3.5 seconds

b. Resuscitated cardiac arrest when not clearly attributable to the drug.

2. Events requiring interruption of titration

Events such as open heart surgery, angioplasty, valve replacement, recurrent myocardial infarction, non-cardiac surgery and aneurysmectomy will require interruption of titration.

If, in the judgment of the investigator, the patient's VPD rates and EF are not significantly altered, the titration may be resumed, where discontinued, at least one week following the event.

If the investigator judges it prudent to obtain new baseline Holter and LVEF, the patient can restart titration. However, any drug for which an adverse effect not alterable by the event had already been demonstrated will be eliminated during the retitration, as will flecainide if the latest LVEF is $<$ 0.30.

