Digitalis, beta blockers, beta agonists, phenothiazines, tricyclic antidepressants, theophylline derivatives, calcium channel blockers, and anticonvulsants might have some effect upon the incidence of ventricular arrhythmias, but the effect is not likely to be a major one. Every effort should be made to maintain constant therapy during titration but changes in the above drugs will not require special procedures or changes in the titration process.

3. Conditions Shown to Be Due to the Drug Requiring Proceeding to the Next Drug in the Sequence.

- a. Arrhythmias producing symptoms. Only serious symptoms such as syncope or presyncope should be considered under this criterion. Palpitations alone would not be regarded as a toxic endpoint.
- b. Sustained ventricular arrhythmias, torsades de pointes or a run of ≥ 15 consecutive VPD's at a rate of $\geq 120/\text{min}$.
- c. Any significant increase in the VPD rate or any significant increase in runs. A significant increase in VPD's includes proarrhythmia, ≥ 1500 VPD's/hr, or other significant increase.

For those patients showing ≥ 5 runs/day on the baseline Holter, a ten-fold increase will be considered a toxic endpoint. For patients with fewer than 5 runs/day on baseline, 50 or more runs will be considered toxicity.

- d. Prolongation of the QTc interval ≥ 1.4 times baseline and/or ≥ 0.6 sec. The rationale for this criterion is based upon the observation that patients showing marked lengthening of the QTc interval in response to antiarrhythmic agents (usually type I agents) seem to be at increased risk of syncope or sudden death.
- e. Development of the following abnormalities in impulse formation or conduction:
 - heart rate < 30 for a period lasting a minimum of 1 minute.
 - any pause ≥ 3.5 seconds.
 - second degree Mobitz type II A-V block.
 - advanced or third degree A-V block.
 - QRS width ≥ 2 times baseline or ≥ 0.20 sec.
- f. Resuscitated cardiac arrest. The patient may proceed to the next CAST drug in the sequence if evidence suggests that the episode is almost certainly due to the drug. However, the investigator can choose to end titration if he does not want to continue through the CAST drug sequence.
- g. Development of new or worsened CHF symptoms which are not controlled by therapy for the CHF and which after washout (of sufficient duration for the drug to be eliminated and the physiology to return to normal) are judged by the investigator to be due to the drug.
- h. Intolerable adverse symptoms.

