Temporary discontinuation of the study drug or conversion to the alternate drugs will be allowed (but is not necessarily required for all conditions) for 4) development of heart block (Mobitz II or complete), 5) development of adverse ECG effects as defined for titration, 6) coronary artery bypass graft surgery and/or other cardiac surgery or non-cardiac surgery, 7) congestive heart failure, 8) apparent proarrhythmia, 9) recurrent myocardial infarction, 10) miscellaneous late adverse effects.

[figure not shown]
For events or conditions in which only temporary discontinuation is needed (4, 6, 9 below and generally in all conditions where washout does not verify the condition), the patient is to be restarted on discontinued CAST therapy as soon as adequately stabilized.

For conditions which are considered likely to be dose related (4, 5, 10 below), and if the patient is on high dose, the investigator will reduce the dose to attempt to resolve the condition. In all other cases or in the event the condition does not disappear on lower dose, the CAST therapy will be withdrawn, and, if the condition is verified by the washout to be drug related, titration will resume on the next drug in the sequence (if any) at the dose level of the current drug. The titration will be blinded and will be directed from the Coordinating Center so that patients randomized to active CAST therapy will resume titration on active therapy and those randomized to placebo will resume titration on placebo. When therapy is found which is tolerated, a Holter will be obtained which will be read at the Holter center (it will not be read locally), and the results will be screened by the Coordinating Center for safety and to document the level of suppression.

After observing any event, the investigator is not required to screen for all possible disqualifying conditions. However, if a disqualifying ECG effect or arrhythmia is observed after washout following an event (even though the patient might have been washed out for a condition presumably unrelated to the disqualifying condition noted), the patient should be assigned to individualized therapy and followed per protocol.

Figure 1

Retitration Schedule

4. Heart block (Mobitz II advanced or complete).

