The drug will be stopped and washed out for a minimum of 4 half-lives of the drug. If block persists and a pacemaker is implanted, CAST drugs should be restarted. Otherwise, the patient will resume titration (see figure 1). If on the high dose, titration will resume by first trying the low dose.
5. Adverse ECG effects.
It is possible that changes on electrocardiogram (besides bradycardia or heart block) could occur which would prompt a reassessment of drug therapy, for example, QT prolongation or QRS prolongation. If the patient develops an intraventricular conduction defect with the QRS duration ≥ 2 times baseline or ≥ 0.20 seconds, or if the QTc interval is ≥ 1.4 times pretreatment or is ≥ 0.6 , which is verified by washout, alteration in drug or dose will be required. The rationale for these criteria is based upon the observation that patients showing marked lengthening of the QTc interval in response to antiarrhythmic agents seem to be at increased risk of sudden death. Development of the following abnormalities in impulse formation or conduction would also be considered adverse ECG effects, although their detection will be sporadic because of the infrequency of the Holter monitoring and followup: heart rate < 30 for a period lasting at least 1 minute or any pause ≥ 3.5 seconds. For all of the above, when verified by washout, the investigator will resume titration if possible (see figure 1). If on the high dose, titration will resume by first trying the low dose.
6. Coronary artery bypass graft surgery and/or other cardiac surgery or non-cardiac surgery.
The CAST therapy will be stopped only for as long as the patient is unable to take medication orally. No other tests are necessary. The patient will be maintained on routine followup as though the surgery never occurred.
7. Congestive heart failure.
Therapy for CHF will be initiated. If CHF is easily controlled, the CAST drug will be continued. If CHF is not easily controlled (i.e., the patient is still symptomatic after therapy for CHF), and if it appears that the drug may be related to heart failure, titration will be resumed if possible (see figure 1). If, however, after withdrawal, the drug does not appear to have caused the CHF, the physician will be encouraged to reestablish the original CAST therapy.

[figure not shown]
8. **Apparent proarrhythmia or excessive VPD's.**

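### Section 9, item 4 (heart block), read literally, sends a patient whose high-grade block persists after washout without a pacemaker back to titration, against the general follow-up rules of the same section

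*Protocol*

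**What the plan says.** Section 9, item 4 requires the drug to be stopped and washed out for at least four half-lives. It then gives the decision: "If block persists and a pacemaker is implanted, CAST drugs should be restarted. Otherwise, the patient will resume titration (see figure 1". A patient on the high dose resumes by trying the low dose first.

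The general paragraphs of Section 9, before the numbered items, set rules for all events in follow-up:

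- Once CAST therapy has been withdrawn, "if the condition is verified by the washout to be drug related, titration will resume on the next drug in the sequence".
- Where only a temporary stop is needed, or washout does not verify the condition, the same therapy is restarted when the patient is stable. Item 4 is named in this list.
- Where a condition is thought likely to be dose related, a patient on the high dose has the dose reduced. Item 4 is named here too.
- After any event, "if a disqualifying ECG effect or arrhythmia is observed after washout following an event", then "the patient should be assigned to individualized therapy and followed per protocol".

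The 1989 Protocol Revision states that nothing changes beyond the revisions it lists. Item 4 is not listed. Revision 10 limits blinded retitration to dose reduction.

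**The concern.** The second sentence of item 4 applies to everything the first does not cover. The first requires two things together: persistent block and an implanted pacemaker. If the block persists and no pacemaker is implanted, the first sentence fails and the second applies, so the instruction is to resume titration.

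That is the wrong way round. Item 4 itself makes a pacemaker the condition for restarting the drug when block persists, yet its wording returns the patient without one to titration. In the active arm this means giving an antiarrhythmic drug again to someone who still has high-grade block and no pacing. Blinded retitration keeps the assigned arm, so a placebo patient would only receive placebo.

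Section 9 says the specifics for each event are in the numbered items. A center managing heart block would therefore be expected to turn to item 4.

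**Working it through.** No figure is involved, so the check is to list the outcomes of item 4 and compare each with the general rules of Section 9.

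| After washout | Pacemaker | Item 4 as written | General rules of Section 9 |
|---|---|---|---|
| Block persists | Yes | Restart CAST drug | Fits the restart rule once the patient is stable |
| Block resolves | No | Resume titration | Fits: washout points to the drug |
| Block resolves | Yes | Resume titration | Fits, for the same reason |
| Block persists | No | Resume titration | Does not fit |

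The last row in detail:

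1. *Next drug in the sequence.* This step depends on washout verifying that the condition is drug related. Block still present after at least four half-lives off drug has not been so verified.
2. *Dose reduction.* This rests on the condition being thought dose related. Persistence with no drug on board argues against that.
3. *Restart of the same therapy.* This requires a stable patient, which unpaced high-grade block hardly describes. In any case it gives restart, not retitration.
4. *Individualized therapy.* This applies to a disqualifying ECG effect seen after washout. The protocol does not define the term. However, entry exclusion 23, listed under ECG criteria in Section 4.B, is "Mobitz II 2nd degree, advanced or 3rd degree AV block noted" from day 6 after the infarction, and the events list in Section 8.C counts heart block among adverse ECG effects. This is the rule that fits.

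Neighbouring items in Section 9 show the condition that item 4 lacks. Item 5 resumes titration when washout verifies the effect. Item 7 does so when the drug may be related to the heart failure. Item 8 changes therapy when proarrhythmia is verified or VPD's are excessive. Item 10 has no such condition of its own and relies on the general rule. Item 5 cannot fill the gap in item 4, because it sets heart block aside.

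The titration-phase rules point the same way, by parallel only. Section 6.G.1.a ends titration permanently for "The appearance of any entry exclusion criteria proven by washout not to be due to drug toxicity". Its relaxations are limited: "For this reason criteria 19, 21, and 22 are modified to" less strict limits, and criterion 23 is not among them. Section 6.G.3 lists the same grades of block under "Conditions Shown to Be Due to the Drug Requiring Proceeding to the Next Drug in the Sequence".

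The 1989 Revision does not settle the matter. With only dose reduction allowed, a patient already on the lowest moricizine dose has no retitration step left, yet item 4 still says titration resumes.

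**The case against.** The best defence is that item 4 is not read alone. The paragraph on disqualifying ECG effects after washout comes shortly before it and covers any event. Restarting is conditional on the absence of contraindications. The study physicians may withdraw medication in the patient's interest. Blinded retitration is directed from the Coordinating Center, although dose reduction, the only step left after 1989, is described as the investigator's. The disputed sentence also refers to Figure 1, which is not available and may contain a branch for this case. And the natural clinical reading treats persistence and pacing as one course, so that the second sentence simply means the block has gone.

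Most of this stands, and it lowers the practical risk. It does not remove the contradiction. The safeguards lead to one action, while the item that is meant to hold the specifics states another.

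A reader might infer that item 4 also breaches Sections 6.G and 6.H. The documents do not support that. Those rules govern titration before randomization; Section 6.G.1 speaks of patients who would not go on to blinded therapy. Section 6.G.1.a also makes no exception for pacemakers, so if it governed follow-up it would forbid the restart of paced patients too. Section 9 has its own rules for randomized patients, and the finding rests on those.

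A reader might also want a number of patients at risk. The protocol does not say how often high-grade block occurs, or how often it persists without a pacemaker. Any count would rest on an assumed incidence of all high-grade block, which is not the affected subset.

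**Conclusion.** The concern holds as a minor contradiction, relevant to safety, between item 4 and the general follow-up rules of Section 9. It concerns one outcome: persistent high-grade block with no pacemaker. Actual re-exposure could occur only in the active arm and, under the 1989 Revision, only where a lower dose is available. The number of patients cannot be estimated from the document.

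The conclusion rests on the written text, without Figure 1, and on taking high-grade AV block to be a disqualifying ECG effect. If that second assumption is refused, titration still lacks the drug-related verification that the general rules attach to it.

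It would go too far to infer that the authors meant to treat unpaced patients with persistent block, since the likely intent was to retitrate when the block resolves. Nor does the point bear on the primary result: analysis is by intention to treat, and alpha, power and sample size do not depend on item 4.

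**What to change.** Keep the instruction to restart when block persists and a pacemaker is implanted. Replace the sentence that follows it with:

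> If block resolves on washout, resume titration if possible (see figure 1; dose reduction only under the 1989 revision). If block persists and no pacemaker is implanted, do not restart or retitrate CAST drug; assign to individualized therapy and follow per protocol.

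Check that Figure 1 shows the same branches. The cost is one sentence. No visits, tests or patients are added, and the outcome is one that Section 9 already provides.

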10. COMPLIANCE

A. Introduction

Compliance to the prescribed medication regimen will be measured by means of monitoring pill counts, and compliance to followup schedules will be measured by means of monitoring dataform submission. Compliance will be maintained at acceptable levels by educational efforts which are designed to inform the patient of his responsibilities to the protocol, to discover causes of noncompliance, and to apply remedies to improve unacceptable compliance.

B. Enhancing Compliance through Patient Education

Patients enrolled into CAST will be evaluated by a brief interview. Evaluation will be made of knowledge concerning cardiac disease and effects of treatment, attitudes concerning participation in the clinical trial, expectations for personal benefit from participation, motivation for compliance with treatment regimens and research protocols, and previous experience with medical treatment for chronic disease.

Following initial evaluation, patients will be instructed in procedures required of them for successful participation. Patients will be provided with a handbook summarizing the main features of the trial and the requirements for participation. Further efforts will be made during each repeat visit to the clinical center to reinforce adherence to the drug regimen and required procedures.

C. Remedies for Noncompliance

Remedies for noncompliance will emphasize early detection of poor compliance through prompt entry into the Coordinating Center computer of compliance monitoring data. Minimum standards for compliance will be established with respect to the performance of individual patients, as well as average values across centers. Patients falling below minimum standards of compliance will be identified by means of monitoring pill counts and adherence to followup schedules as recorded in the database, and the Coordinating Center will notify centers of problems. Coordinators should be alerted to possibilities of poor compliance in association with dosage increases, changes in regimen, toxic adverse effects, multiple drug regimens, and frequent clinic appointments (especially in early phases of the study). Behavioral techniques to remedy noncompliance can include using goals and positive reinforcement to establish desired levels of adherence and recruitment of social support for increasing motivation. No patient will be dropped because of poor compliance, and thus continued effort to enhance compliance will be required throughout the duration of the study.

When patients do drop out of the study, intensive efforts, including contact by telephone and in person, will be made to retrieve them. Experience gained from compliance-enhancement strategies of coordinators participating in other clinical trials, as well as those used successfully by CAST coordinators, will be discussed at coordinator meetings.

2. Breaking the code because of concern that the therapy may be jeopardizing patient safety.

If the investigator or the patient's private physician believes that patient safety requires unblinding, the following procedures should be followed:

- a. The details of the particular case should be discussed among the Clinical Center staff and the personal physician. In most instances, it will be found that drug discontinuation, followed by usual medical treatment, will provide optimal care. If such care entails the use of an antiarrhythmic agent, such an agent can often be administered without knowing whether the discontinued study drug was active or placebo.
- b. If it is thought that medical care can be improved by knowledge of the treatment, that decision can be discussed with [name] at the Coordinating Center. It may be possible for a physician who does not see study patients to be unblinded, and advice regarding such care could be made by this physician after determining the therapy. This physician should avoid disclosing the study drug identity to other staff or to the patient's personal physician.
- c. If the decision is made that the patient's best interest requires that the Clinical Center staff have knowledge of the study drug, either directly or indirectly through advice of the physician mentioned in (b.) above, the patient will be considered to be on individualized therapy from that point on. It will usually be unnecessary for all staff to be unblinded. The staff that are unblinded are urged to preserve the confidentiality of the information.
- d. Regardless of the nature and degree of unblinding, the patient should continue to be followed on the usual visit schedule for the duration of the study. If at all possible, since analysis will be by intention to treat, the individualized therapy should be the study drug.
- e. Unblinding can be done by:
 1. On working days, between the hours of 8:00 am and 5:00 pm Pacific Time, a call should be placed to the Coordinating Center. If a physician other than a CAST investigator will break the blind, it is preferable for the coordinator or CAST investigator to call ahead and alert the Coordinating Center for the expected call if this is possible. The caller should have the patient I.D. number.

The phone number to call is [contact].

2. At other times, the Drug Distribution Center's 24-hour answering service can be called. The caller should ask for the pharmacist on call for the Cooperative Studies Program Research Pharmacy, identify the CAST study, and have the patient I.D. number or X-bottle number.

The phone number to call is [contact].

3. If necessary, the unblinding envelopes, which will be maintained at each center, may be opened to provide the information. In this case, the opened envelope, with information on the unblinding (reason unblinded, date unblinded) should be sent to the Coordinating Center. (At the end of the study all unblinding envelopes must be accounted for and all opened envelopes must be explained.)

f. Every case of unblinding must be reported to the Coordinating Center.

E. Confidentiality

It must be stressed to all Clinical Center personnel that confidentiality of patient information must be preserved. No unauthorized personnel should have access to patient records or results of interviews or tests. All record storage rooms should be appropriately secured and should contain any necessary locked files or other storage equipment.

No identifiers will be sent to the Drug Distribution Center or NHLBI. Name and social security number will be sent to the Coordinating Center, but these will be kept separate from the main database. The only use of these data will be to conduct future inexpensive and non-invasive long-term mortality followup by National Death Index searches. All communication about patients will utilize numerical and alphabetical codes by which central study files may be linked to individual patients. The Clinical Centers will retain forms which permit such linkage. These Patient Identification Forms contain patient identifiers and the study codes. The forms are securely kept at the Clinical Centers. If, in the future, it is necessary for patient safety reasons to contact individual patients, these locally maintained forms will allow such contact.

